11. MEASUREMENT OF EFFECT

All Patients will undergo CT or MR prior to returning for cycle 2 of the investigational treatment (approximately week 6 or 7), at the time of the off treatment visit at MD discretion, and subsequently based upon the timing the regular care for their cancer. Response or progression will primarily be evaluated by CT or MR imaging of tumor nodules using RECIST criteria v1.1, however tumor measurements are not required as patients must be completely surgically resected to be eligible.

11.1 Disease Parameters (May be used as a guideline for scan review prior to Cycle 2)

Measurable disease: Measurable lesions are defined as those that can be accurately measured in at least one dimension (longest diameter to be recorded) as ≥ 10 mm with CT or MR imaging (CT/MR slice thickness no greater than 5 mm). Malignant lymph nodes may be considered measurable disease if they are ≥ 15 mm in short axis as measured by CT or MR imaging with no greater than 5 mm slice thickness.

Non-measurable disease: All other lesions (longest diameter < 10 mm with CT or MR scan) are considered non-measurable disease. Bone lesions, ascites, leptomeningeal disease, pleural/pericardial effusions, lymphangitis cutis/pulmonis, inflammatory breast disease are all non-measurable.

11.2 CT or MR-Imaging Response Criteria

CT or MR imaging will be performed with cuts of 5 mm or less in slice thickness contiguously. RECIST criteria v1.1 will primarily be used to assess tumor recurrence.

Progressive Disease (PD): The appearance or recurrence of one or more new lesions is considered progression.

11.3 Duration of Response

Time-to-Progression (TTP): Time-to-Progression is measured from the start of treatment until the criteria for progression are met

Duration of overall response: The duration of overall response is measured from the time of surgical resection until the first date that progressive disease is objectively documented (taking as reference for progressive disease the smallest measurements recorded since the treatment started).

12. DATA REPORTING / REGULATORY REQUIREMENTS

12.1 Data Safety Monitoring Plan

Sponsor, Investigator, Sub-investigators, regulatory, CRS management, clinical research coordinators, clinical research associates, data managers, and clinic staff meet monthly in disease center Data Safety Monitoring Boards (DSMB) to review and discuss study data to include, but not limited to, the following:

- serious adverse events
- subject safety issues
- recruitment issues
- accrual
- protocol deviations
- unanticipated problems
- breaches of confidentiality

Minutes from the DSMB meetings are available to anyone unable to attend the center DSMB.

All toxicities encountered during the study will be evaluated on an ongoing basis according to the NCI Common Toxicity Criteria version 4. All study treatment associated adverse events that are serious, at least possibly related and unexpected will be reported to the IRB. Any modifications necessary to ensure subject safety and decisions to continue, or close the trial to accrual are also discussed during these meetings. If any literature becomes available which changes the risk/benefit ratio or suggests that conducting the trial is no longer ethical, the IRB will be notified in the form of an Unanticipated Problem submission and the study may be terminated.

All study data reviewed and discussed during these meetings will be kept confidential. Any breach in subject confidentiality will be reported to the IRB in the form of an Unanticipated Problem submission. The summaries of these meetings are forwarded to the UPCI DSMC which also meets monthly following a designated format.

For all research protocols, there will be a commitment to comply with the IRB's policies for reporting unanticipated problems involving risk to subjects or others (including adverse events). DSMC progress reports, to include a summary of all serious adverse events and modifications, and approval will be submitted to the IRB at the time of renewal.

Protocols with subjects in long-term (survival) follow-up or protocols in data analysis only, will be reviewed twice a year rather than monthly by the disease center DSMB.

Both the UPCI DSMC as well as the individual disease center DSMB have the authority to suspend accrual or further investigate treatment on any trial based on information discussed at these meetings.

All records related to this research study will be stored in a locked environment. Only the researchers affiliated with the research study and their staff will have access to the research records.

12.2 Quality Control and Quality Assurance

Independent monitoring of the clinical study for protocol and Guidelines on Good Clinical Practice compliance will be conducted periodically (i.e., at a minimum of annually) by qualified staff of the Education and Compliance Office – Human Subject Research, Research Conduct and Compliance Office, University of Pittsburgh.

The Investigator (i.e., the study site principal investigator) and the University of Pittsburgh and University of Pittsburgh Medical Center will permit direct access of the study monitors and appropriate regulatory authorities to the study data and to the corresponding source data and documents to verify the accuracy of this data.

12.3 Data Handling and Record-Keeping

The Investigator (i.e., the study site principal investigator) will maintain records in accordance with Good Clinical Practice.

The investigator will retain the specified records and reports for up to 2 years after the marketing application is approved for the investigational drug; or, if a marketing application is not submitted or approved for the investigational drug, until 2 years after investigations under the IND have been discontinued and the FDA so notified.

12.4 Institutional Review Board (IRB) Approval

The investigator (i.e., the study site principal investigator) will obtain, from the University of Pittsburgh Institutional Review Board (IRB), prospective approval of the clinical protocol and corresponding informed consent form(s); modifications to the clinical protocol and corresponding informed consent forms, and advertisements (i.e., directed at potential research subjects) for study recruitment, if applicable.

The only circumstance in which a deviation from the current IRB-approved clinical protocol/consent form(s) may be initiated in the absence of prospective IRB approval is to eliminate an apparent immediate hazard to the research subject(s). In such circumstances, the investigator will promptly notify the University of Pittsburgh IRB of the deviation.

The University of Pittsburgh IRB operates in compliance with FDA regulations at [21 CFR Parts 50](#) and [21 CFR 56](#), and in conformance with applicable International Conference on Harmonization (ICH) Guidelines on Good Clinical Practice.

In the event that the University of Pittsburgh IRB requires, as a condition of approval, substantial changes to a clinical protocol submitted under an FDA-accepted IND application, or in the event of an sponsor's decision to modify the previously accepted clinical protocol, the sponsor will submit (i.e., in advance of implementing the change) a Protocol Amendment to the IND describing any change that significantly affects the safety of subjects, the scope of the investigation, or the scientific quality of the study. Examples of protocol changes requiring the submission of a Protocol Amendment include:

- Any increase in drug dosage or duration of exposure of individual subjects to the investigational drug beyond that described in the current protocol, or any significant increase in the number of subjects under study.
- Any significant change in the design of the protocol (such as the addition or deletion of a control group).
- The addition of a new test or procedure that is intended to improve monitoring for, or reduce the risk of, a side effect or AE; or the dropping of a test intended to monitor the safety of the investigational drug.

12.5 Ethical and Scientific Conduct of the Clinical Study

The clinical study will be conducted in accordance with the current IRB-approved clinical protocol; ICH Guidelines on Guidelines on Good Clinical Practice; and relevant policies, requirements, and regulations of the University of Pittsburgh IRB, University of Pittsburgh and University of Pittsburgh Medical Center, Commonwealth of Pennsylvania, and applicable federal agencies.

12.6 Informed Consent

The investigator (i.e., the study site principal investigator) will make certain that an appropriate informed consent process is in place to ensure that potential research subjects, or their authorized representatives, are fully informed about the nature and objectives of the clinical study, the potential risks and benefits of study participation, and their rights as research subjects. The investigator, or a sub-investigator(s) designated by the sponsor, will obtain the written, signed informed consent of each subject, or the subject's authorized representative, prior to performing any study-specific procedures on the subject. The date and time that the subject, or the subject's authorized representative, signs the informed consent form and a narrative of the issues discussed during the informed consent process will be documented in the subject's case history. The investigator or sub-investigator will retain the original copy of the signed informed consent form, and a copy will be provided to the subject, or to the subject's authorized representative.

The investigator will make certain that appropriate processes and procedures are in place to ensure that ongoing questions and concerns of enrolled subjects are adequately addressed and that the subjects are informed of any new information that may affect their decision to continue participation in the clinical study. In the event of substantial changes to the clinical study or the risk-to-benefit ratio of study participation, the investigator will obtain the informed consent of enrolled subjects for continued participation in the clinical study.

13. STATISTICAL CONSIDERATIONS

13.1 Study Design/Endpoints

13.1.1 Primary endpoint

- (For Phase 1) Define Recommended Phase 2 Dose (RP2D)

- To evaluate time-to-progression (TTP) in patients with peritoneal surface malignancies (PSM), including but not limited to malignant peritoneal mesothelioma and peritoneal carcinomatosis (PC) of appendiceal and colorectal primary tumors. For patients who will be completely resected, time-to-progression will be equal to recurrence.

13.1.2 Secondary endpoints

- To estimate overall survival (OS).
- Correlative studies to characterize sequential immune response changes by quantitative measures of immune cellular phenotypes and chemokine patterns in peripheral blood (see Section 9). These results will be correlated with TTP, PFS, and OS.

Note the additional discussion of the Phase 1 dose-finding studies described in Section 5.1.

13.2 Power and Sample Size for the Study of Efficacy

Based on information from our prospective database at the University of Pittsburgh over the last 10 years, we expect to treat ~ 115 patients per year (malignant peritoneal mesothelioma ~ 15 cases/year; appendiceal peritoneal carcinomatosis ~ 40 cases/year; colorectal carcinomatosis ~ 60 cases/year). We anticipate approximately 50% of treatment patients will participate in the clinical trial. A review of the literature demonstrates median time-to-progression of 20 months, 20 months and 12 months for malignant peritoneal mesothelioma, appendiceal peritoneal carcinomatosis, and colorectal carcinomatosis, respectively. We aim to demonstrate a 25% improvement in time-to-progression (malignant peritoneal mesothelioma 25 months; appendiceal peritoneal carcinomatosis 25 months; and colorectal carcinomatosis 15 months). We will need 168 patients over 3 years of accrual with an additional 1.5 years of follow-up after accrual ceases. This will provide 90% power to detect an overall improvement of 25% for an exponential test at alpha = 0.10.

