3.1 Pre-surgery Eligibility

1. Histologically confirmed peritoneal surface malignancies, including but not limited to malignant peritoneal mesothelioma and peritoneal carcinomatosis (PC) from presumed appendiceal and colorectal primary tumors.
2. The following malignancies are ineligible for this study: low grade appendiceal and pseudomyxoma peritonei.
3. Clinically indicated for optimal CRS+HIPEC
4. At least 18 years of age
5. Able to understand and willing to sign a written informed consent document

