13.3 Data Analysis

At the completion of follow-up in evaluable patients, we will estimate progression-free survival by the Kaplan-Meier method with Greenwood 90% confidence intervals. We will conduct a formal test of the hypothesis that progression-free survival is improved with the experimental therapy. This test will be a one sided exponential test at $\alpha = .10$ that the median progression-free survival is better than 25% compared to historical controls. If this test is significant we will conclude that the progression-free survival is improved compared to the historical control. Descriptive summaries will be prepared of all adverse events by grade, frequency and attribution. An assessment of the association between immune parameters and survival will be conducted. The panel of immune parameters will be tested for association with progression-free and overall survival with Cox proportional hazards regression.

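### The null of the single-arm primary test is not fixed: three historical medians, one unnumbered comparator, and a phrase that can be read as a null ratio of 1.25

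*Combined protocol and SAP*

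**What the plan says.** Section 13.2 takes from the literature a "median time-to-progression of 20 months, 20 months and 12 months for malignant peritoneal mesothelioma, appendiceal peritoneal carcinomatosis, and colorectal carcinomatosis, respectively". It pairs each with its own target: "malignant peritoneal mesothelioma 25 months; appendiceal peritoneal carcinomatosis 25 months; and colorectal carcinomatosis 15 months". The ratio is 1.25 in every case. The size follows: "We will need 168 patients over 3 years of accrual with an additional 1.5 years of follow-up after accrual ceases". Power is then claimed once, for the cohort as a whole: "This will provide 90% power to detect an overall improvement of 25% for an exponential test at alpha = 0.10".

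The expected case mix appears only in the accrual estimate: about 15 mesothelioma cases a year, then "appendiceal peritoneal carcinomatosis ~ 40 cases/year; colorectal carcinomatosis ~ 60 cases/year". It is not described as a set of weights.

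Section 13.3 specifies one one-sided exponential test at 0.10 that "the median progression-free survival is better than 25% compared to historical controls". The decision rule reads: "If this test is significant we will conclude that the progression-free survival is improved compared to the historical control". No historical value is attached to the test.

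Section 3.1 leaves the population open: "Histologically confirmed peritoneal surface malignancies, including but not limited to malignant peritoneal mesothelioma". Tumour types beyond the three have no historical median anywhere in the document.

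**The concern.** In a single-arm trial the historical value is the only comparator, so the null is the hypothesis. Here it could be one pooled median, obtained in any of several ways, or a separate median for each type with a common ratio. These choices give different answers on the same data. If the choice is left until the results are known, it can decide the result.

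A single pooled median also ties the error rates to the mix that happens to enrol, because colorectal patients are expected to progress sooner than the others with or without a treatment effect.

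The null ratio is a second gap. Taken literally, the hypothesis in 13.3 is an improvement exceeding 25%, which makes 1.25 the value to be rejected. The next sentence of 13.3 and the power statement in 13.2 both fit a null of 1.0.

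**Working it through.** **Inputs.** One-sided alpha 0.10, power 0.90, ratio 1.25, medians 20/20/12, mix 15:40:60 of 115 a year, 168 patients, 36 months of accrual plus 18 of follow-up (13.2 and 13.3). Assumed, because not stated: uniform accrual, no dropout, exponential times within type, all 168 analysed.

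**Events.** D = [(1.2816 + 1.2816)/ln 1.25]² = 131.9, so 132.

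**Event probability.** For median m and L = ln 2/m, P(m) = 1 − [exp(−18L) − exp(−54L)]/(36L).

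**Reproducing 168.** The standard calculation divides D by P at the alternative median. For the colorectal type alone (12 to 15 months), P = 0.788 and N = 167.4, which rounds up to 168. Other nulls, with P taken under the alternative and then under the null:

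| Null | N, P under alternative | N, P under null |
|---|---|---|
| 12 months | 167.4 | 155.0 |
| 14.84 (from the average hazard: 115/(15/20 + 40/20 + 60/12)) | 183.4 | 166.8 |
| 15.17 (median of the mixture) | 185.3 | 168.2 |
| Type-specific 20/20/12 | 187.0 | 170.0 |
| 15.83 (weighted mean: (55×20 + 60×12)/115) | 189.1 | 171.1 |
| 17.33 (unweighted mean) | 198.1 | 177.8 |
| 20 months | 214.2 | 190.2 |

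So 168 is informative. It matches 12 months under the usual formula and does not fit 17.33 or 20 under either. It is not conclusive, because the null-based variant gives about 167 to 171 for the weighted and type-specific nulls. Planned accrual of 115 × 0.5 × 3 = 172.5 is also close to 168.

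**Operating characteristics.** Simulation at n = 168, with each patient's type drawn at random from the planned mix. The statistic is log(E/d)·√d, rejecting above 1.2816, where d is observed events. E is expected events: total follow-up × ln 2/m₀ for a pooled null m₀, or the sum of each patient's follow-up × ln 2/(median of that patient's type). The null ratio is 1.0.

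| Null | Type I error | Power at true ratio 1.25 |
|---|---|---|
| 12 months for all | 0.94 | above 0.99 |
| 14.84 | 0.195 | 0.94 |
| 15.17 | 0.134 | 0.90 |
| 15.83 | 0.055 | 0.79 |
| Type-specific | 0.094 | 0.88 |

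**Check on the type-specific row.** P under the alternative, averaged over the mix, is 0.7057, so 168 × 0.7057 = 118.6 events. The normal approximation gives Φ(0.2231 × √118.6 − 1.2816) = Φ(1.148) = 0.875; simulation gives 0.88. Power of 0.90 needs 187 patients by the standard formula and about 183 by simulation.

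**Null ratio 1.25.** With type-specific nulls and a true ratio of 1.25, the trial sits on the null boundary, so rejection is close to the test's size: 0.093 to 0.095 by simulation, against the 0.90 claimed in 13.2.

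**The case against.** The strongest reply is that 13.2 already implies the benign reading. Each historical median is paired with its own target, no pooled value appears, and the common 25% is called overall. Type-specific nulls with one ratio are the natural interpretation, and they bring the error rates close to those stated. The wording about 25% in 13.3 looks like loose drafting, since the sentences around it speak only of improvement. The pooled values in the tables are constructions from the 13.2 inputs and are not in the plan.

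Most of this stands, and it limits the point. It does not remove it, because 13.3, which governs the analysis, names one median and no comparator value. Even the favourable reading gives about 0.88 rather than 0.90.

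Three stronger inferences should be resisted. A reader might infer from the exact match that the sponsor tested or sized against 12 months for everyone. The document does not say so, its type-specific medians argue against it, and other routes lead to nearly the same size. A reader might infer the opposite, that 168 says nothing about the null; that also goes too far, since several nulls do not fit. And a reader might conclude that type I error is inflated. That follows only under some pooled nulls, and the plan adopts none of them.

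**Conclusion.** The omission is certain from the text: neither the historical value nor, unambiguously, the null ratio of the primary test is stated. Its consequence ranges from small to decisive, depending on the null applied. Type-specific nulls give type I error about 0.09 and power about 0.88. Pooled nulls between 15.83 and 14.84 months give type I error 0.055 to 0.20 and power 0.79 to 0.94. A 12-month null for all patients gives type I error about 0.94. A literal null ratio of 1.25 contradicts the 90% power in 13.2.

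The figures assume the planned mix, uniform accrual, exponential times within type, no dropout and 168 patients analysed. The last is not assured: 5.2 (missed windows, late priming), 5.5 (removal from treatment) and 8.1.2 (low cell number) take patients out of the primary analysis. Actual power may therefore be below 0.88. The gap between 0.88 and 0.90 is minor; the undefined comparator is what should be settled before analysis.

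**What to change.** In 13.3:

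- State that the null ratio is 1.0, and replace the phrase about exceeding 25% with one saying that the median is greater than the historical control.
- Make the primary test a one-sample exponential test with type-specific nulls: E = sum over patients of follow-up time × ln 2/(historical median of that patient's type), d = observed events, statistic log(E/d)·√d, one-sided 0.10.
- Report any tumour type descriptively only, unless a historical median for it has been set before analysis.

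In 13.2, restate power as about 0.88 for 168 analysed patients under uniform accrual and no dropout. Note that it will be lower if the exclusions in 5.2, 5.5 and 8.1.2 reduce that number.

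The cost is a few sentences. The test uses only medians already in 13.2 and accounts for differences in enrolled mix among those three types. The drawbacks are a slightly less favourable power statement and the loss of types without a median from the formal test. If 90% is to be kept, simulation under the same assumptions gives about 183 analysed patients (183/57.5 = 3.18 years, about 2 months beyond the planned 3 years of accrual), or 168 patients with about 27 rather than 18 months of follow-up.

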5.9 Duration of Follow Up

Patients will be followed until death and the follow-up information for trial reporting will be obtained either from the patient's medical records or through direct contact with the patient (i.e. clinic visit or phone call). The timing of these will be based on scheduling of clinical care for the treatment of the patient's cancer (i.e. clinic visits every 3 months, 6 months, yearly). Patients will be followed specifically for evidence of progression/recurrence based on imaging and survival.

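### The 90% power for 168 patients counts events at the historical medians; at the target medians about 119 of the 132 required events are expected, and power is about 88%

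*Combined protocol and SAP*

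**What the plan says.** Section 13.2 takes from the literature a "median time-to-progression of 20 months, 20 months and 12 months for malignant peritoneal mesothelioma, appendiceal peritoneal carcinomatosis, and colorectal carcinomatosis, respectively". It sets the aim in these words: "We aim to demonstrate a 25% improvement in time-to-progression", which gives target medians of "malignant peritoneal mesothelioma 25 months; appendiceal peritoneal carcinomatosis 25 months; and colorectal carcinomatosis 15 months". It then plans 168 patients over 3 years of accrual with 1.5 years of follow-up after accrual closes, and concludes: "This will provide 90% power to detect an overall improvement of 25% for an exponential test at alpha = 0.10". Section 13.3 makes the test one-sided. No event target is given, and neither section says at which medians the expected events were counted.

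The analysis is to be done "At the completion of follow-up in evaluable patients". Sections 5.2 (missed treatment windows, late priming), 5.5 (patients removed from treatment) and 8.1.2 (low cell numbers) take some patients out of the primary efficacy analysis. Section 3 says that a recruited patient who is excluded or resigns is replaced. Section 5.9 states: "Patients will be followed until death".

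**The concern.** The power of an exponential test comes from the number of events, but the plan fixes patients and calendar time instead. If the treatment works as hoped, progressions come later and fewer are seen by a fixed cut-off. A calculation that pairs a 25% effect with the event count expected under no effect therefore overstates power. A negative result would be read against a stated 10% chance of missing a true 25% improvement when the actual chance is somewhat higher. The allowance for patients who drop out of the primary analysis also bears on this, because Section 13.2 shows no inflation of 168 for them.

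**Working it through.** **Inputs from Sections 13.2 and 13.3.** One-sided alpha 0.10; power 90%; median ratio 1.25 in a single arm against fixed historical values; null medians 20/20/12 months; target medians 25/25/15 months; clinic cases 15/40/60 of 115 per year; N = 168; accrual A = 36 months; follow-up F = 18 months.

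**Assumptions not in the documents.** Accrual is uniform, and trial patients have the clinic's mix. The null hypothesis is taken as the historical medians themselves, as in the sample-size section.

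**1. Events required.** d = ((z₀.₉₀ + z₀.₉₀)/ln 1.25)² = (2 × 1.2816/0.2231)² = 131.9, so 132.

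**2. Probability of an event.** With λ = ln 2/median, P = 1 − [exp(−λF) − exp(−λ(A+F))]/(λA):

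| Median (months) | P(event) |
|---|---|
| 20 (null) | 0.694 |
| 12 (null) | 0.851 |
| 25 (target) | 0.616 |
| 15 (target) | 0.788 |

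**3. Reproducing the plan.** The overall null median of the mixture solves (55/115)·2^(−t/20) + (60/115)·2^(−t/12) = 0.5, giving t = 15.17 months. At that median, 168 patients yield 131.8 events, power is 90.0%, and N for 131.9 events is 168.2. Summing the strata instead gives (55/115 × 0.694 + 60/115 × 0.851) × 168 = 0.776 × 168 = 130.4 events and 89.7%. Either way the stated figures are recovered from null-hazard events.

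**4. Events at the target medians.** (55/115 × 0.616 + 60/115 × 0.788) × 168 = 0.7057 × 168 = 118.6.

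**5. Power with those events.**
- Normal approximation on the log scale: Φ(0.2231 × √118.6 − 1.2816) = Φ(1.148) = 87.5%.
- Exact chi-square with 119 events: 87.6%.
- Null variance for the critical value and alternative variance for power: 88.4% to 88.6%.
- Simulation (40,000 trials) of the log test: 87.9% at an actual alpha of 0.093; about 88.5% when calibrated to alpha 0.10.
- Simulation of the chi-square test: 89.0% at an actual alpha of 0.103.

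**6. Sensitivity to case mix (normal approximation).** No colorectal patients: 103.5 events, 83.9%. All colorectal: 132.4 events, 90.1%.

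**7. What would restore 90% (normal approximation).** 131.9/0.7057 = 187 patients on the same schedule, or 168 patients with 27.2 months of follow-up after accrual, which is 27.2 − 18 = 9.2 months longer.

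**8. Unreplaced losses from the primary analysis.** The rates are assumed, because the documents give none. Multiplying 118.6 by the share retained and using the normal approximation:
- 5% loss: 112.6 events, 86.1%.
- 10% loss: 106.7 events, 84.7%.
- 20% loss: 94.8 events, 81.4%.

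**9. Room for replacement.** Expected accrual is 115 × 50% × 3 = 172.5 patients, 4.5 above 168, or about 3%.

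**The case against.** The strongest reply is that the sponsor's figure is not a slip in calculation. It reproduces almost exactly with events taken at the null hazard, and the plan names only an exponential test, without a variance convention. Some forms of that test come within about a point of 90%. The historical medians are round literature values in a single-arm phase 2 trial, so a point or two may look immaterial. The trial's mix may also be more favourable than the clinic's: Section 3.1 excludes low-grade appendiceal disease and pseudomyxoma. If half the appendiceal cases were ineligible for that reason (an assumption), there would be 121.7 events and 88.1% power.

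Much of this stands, and it limits the size of the point. It does not remove it: reproducing 168 suggests where the number came from, but that route combines a 25% effect with the event count of no effect, and every form of the test in step 5 falls below 90% at the plan's own mix.

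A reader might also infer that the trial is seriously underpowered because many patients will be dropped from the primary analysis. The documents do not support that. They give no exclusion rate, and Section 3 provides for replacement. What remains is uncertainty. The Section 3 rule does not clearly cover a patient who stays on treatment but is left out of the primary analysis under Sections 5.2 or 8.1.2. Projected accrual leaves little room for replacements. The monitoring table in Section 13.4 ends at 168 and speaks of enrolled patients, which hints that 168 is not a count of evaluable patients but does not settle it.

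**Conclusion.** The point holds, at modest size. The stated 90% depends on counting events at the historical medians. At the target medians, about 119 events are expected against 132 required, and power is about 88% (87.5% to 89% by form of test) if all 168 patients are evaluable. That rests on uniform accrual and the clinic's mix; the range across mixes, 83.9% to 90.1%, is wider than the range across tests. Any further loss from non-evaluable patients is conditional on a rate and a replacement practice that the documents leave open. It would be too strong to say that the plan's inputs cannot yield its figure, or that power is known to be in the low 80s.

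**What to change.** In Section 13.2, give power as about 88% for 168 evaluable patients, with expected events based on the target medians and the 132-event requirement stated. Name the form of the exponential test and the assumed accrual pattern and case mix. Say whether 168 counts enrolled or evaluable patients, and whether the replacement rule in Section 3 covers patients removed from the primary analysis under Sections 5.2, 5.5 and 8.1.2. If it does not, show power under stated loss rates. This costs a few sentences and a slightly less favourable figure.

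Optionally, time the final analysis at 132 events. Under the target medians that falls about 27 months after accrual ends. Section 5.9 already follows patients for progression and survival until death, so no new kind of data is needed; the cost is a delay of about 9 months. Enrolling about 187 evaluable patients on the present schedule would also restore 90%, but it exceeds the 172.5 patients that the plan's own accrual projection provides.
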